Design overview. Groups of 3-5 clinicians were recruited by each agency leader. Once all clinicians at an agency were enrolled, they had a 2-week initial training period in which they completed the Project ImPACT Beginner e-Course, a 6-hour self-directed online tutorial on Project ImPACT intervention content. The Beginner e-Course consisted of didactic modules with slides and audio recordings about Project ImPACT NDBI intervention strategies and best practices for collaborating with parents. Modules included video examples of caregivers implementing the intervention strategies and periodic quizzes about course content, but did not include explicit instruction about parent coaching.

Following the initial training period, clinicians entered the Baseline Phase (3 to 9 weeks; randomized by agency) during which they were asked to follow the Project ImPACT coaching manual and meet weekly with their enrolled families, but did not receive consultation support. After the baseline phase, all enrolled clinicians at each agency entered the consultation phase, during which they received 12 group consultation sessions, once per week, for 1.5 hours per session. The consultation phase included three, 4-week blocks in which the group completed one consultation training activity per block (i.e., case support, skill rehearsal, or feedback on

videotaped sessions). Clinicians submitted recordings of all Project ImPACT telehealth sessions throughout the Baseline and Consultation phases, and then again at Follow Up (8-weeks post consultation). Information about the procedures used in each phase is outlined below.

Baseline phase. Clinicians received an e-book copy of the Project ImPACT Coaching Manual, which includes detailed descriptions about the theoretical underpinnings of the intervention and lesson plans for each of the 24 sessions (e.g., session agendas, handouts, access to video models of NDBI intervention strategies, examples of trouble-shooting tips for common challenges with clients). Clinicians also received an e-book copy of the Project ImPACT Parent Manual, which includes descriptions of the NDBI strategies in parent-friendly language and tips about how to apply NDBI strategies at home and in the community. Clinicians were instructed to follow the lesson plans in the Project ImPACT coach manual and no consultation support was provided during the Baseline phase.

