Methodological challenge with the baseline phase. The research team became aware of a methodological flaw following visual analysis of manual adherence data from the first 4 agencies. Within-condition visual analysis indicated that baselines across agencies were unstable due to inflation of the manual adherence scores for the first 2 sessions of Project ImPACT, as compared to sessions 3-24. Conceptually, this made sense because these 2 sessions were atypical and did not include instruction on NDBI techniques nor an active parent coaching component in which clinicians provided feedback; session 1 was an overview of the program and session 2 was a goal setting session. Both sessions are much less complex than the other parent coaching sessions. Agencies #1-4 had started data collection by this point, and due to the initial randomization procedure using parameters of 3-6 weeks of baseline, only 1 agency had at least 3 weeks of usable baseline sessions (Agency #2). For this reason, an additional 2 agencies were recruited (Agencies #5 and #6), and baseline lengths for those agencies were randomized for 6-9 weeks to ensure that baseline lengths had at least 3 usable Project ImPACT sessions. Additionally, to allow for the retention of all clinicians in Agencies #5 and #6, baselines for those two agencies were extended by 1 week to allow for clinicians who had multiple cancellations in the baseline period to acquire at least 2 usable baseline sessions.

Consultant Fidelity to Consultation Conditions

Consultant fidelity to the three consultation conditions was assessed by 2 coders naïve to condition and timepoint using the Project ImPACT Consultation Adherence Checklist. The checklist included scores for the percentage of required training activities for each of the 3 consultation components, as well as the length of time spent on the training activities (e.g., time

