Feedback. On average, Feedback sessions were implemented with 97% fidelity, with no time spent on Skill Rehearsal or Case Support activities. Consultation sessions included an average of 18:09 minutes spent watching Project ImPACT session videotapes (range: 0 seconds to 26:06 minutes), 38:20 minutes spent on performance feedback (range: 0 seconds to 48:31 minutes), 1:57 minutes spent on feedback about technology support (range: 0 seconds to 7:23 minutes), and 2:08 minutes spent on feedback about the use of program materials (range: 0 seconds to 8:13 minutes).

Data Collection for Observational Measures of Clinician Fidelity

Clinicians recorded all telehealth sessions with enrolled families and submitted the video recordings via a HIPAA-compliant Dropbox link. There was a high frequency of session cancellations across the study, which is common in the community mental health system. For the 3 agencies with sufficient baseline lengths, 76 sessions of the 299 scheduled sessions were canceled (25.4%).

Fidelity. Adherence and competency were measured independently, as research suggests that providers may adhere to manual content without demonstrating appropriate competence in the delivery of the content (Cross & West, 2011). For instance, a less competent provider could give constructive feedback to a caregiver, but might do so in a way that is too harsh, making the comments unhelpful. In that case, they might be adhering to procedural requirements of a manualized parent coaching program like Project ImPACT (i.e., providing constructive coaching comments), but the clinician's approach would be at low competency. Furthermore, it is possible that manual adherence may be related to a cognitive mechanism of consultation (e.g., proceduralization), while competency may be related to a skill mechanism (i.e., quality at which an intervention is delivered).

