3 agencies with sufficient baseline data were used for Aim 1 analysis. A summative between conditions visual analysis was used to evaluate changes in data patterns (changes in level, trend, and variability from one condition to the adjacent condition; Barton et al., 2018, p. 190). We conducted a visual analysis for each agency (using weekly data averaged across all clinicians at the agency). Hypotheses about the presence of a functional relation were tentatively confirmed or rejected based on whether the consultation component was associated with a change in level from one condition to the subsequent condition. We hypothesized that consultation components would be associated with a change in level from condition to condition. Less emphasis was placed on trends and changes in trend direction because we did not have any hypotheses that scores would vary within a 4-week period due to the effect of time. Thus, change in level was the main indication of a significant finding; however, if there was a clear and meaningful shift in trend direction (e.g., steep decelerating trend to gradual accelerating trend but no change in mean level), this was also used when determining which phase changes were considered significant. This effect needed to be replicated across all 3 agencies (inter-case replication) for the functional relation to be tentatively confirmed; recommendations for interpreting single-case designs suggest that an effect should be replicated across at least 3 cases.

Ideally, a functional relation should be confirmed when there is evidence of both *intra*-case and *inter*-case replication (Barton et al., 2018). Resource limitations prevented our research design from demonstrating replicated effects within agencies (intra-case replication) – this would require multiple baseline phases and multiple conditions of each consultation component, resulting in a consultation period that would last well beyond the present 3-month duration and thereby make participant recruitment and retention unlikely. Therefore, any functional relations

that were identified in this study could only be labeled as “tentatively confirmed” if inter-case replication was found.

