and 2) *participant-specific* parameter estimates that demonstrate the effect of consultation components on an individual clinician's fidelity scores. First, estimates for the 2-level model (averaging across clinicians) include estimated fixed effects for each consultation component and random deviations for each clinician. These deviations are obtained from the random effect estimates, which included an intercept for each clinician and a random component for each of the 3 consultation phases. These random effects for the intercept allow the model to vary for each clinician in regard to their baseline fidelity level. The random effects for each consultation component allowed for the estimated effects of each consultation component to vary across clinicians (e.g., the effect of feedback could have a stronger magnitude for clinician 0201 than 0502). Next, the participant-specific parameters are estimated using the fixed and random effect estimates from the 2-level model. They are a combination of fixed effects and the between-participant variance. These participant-specific parameters quantify the effects of each consultation component on an individual clinician's fidelity levels. However, the model does not compute tests of statistical significance for effects of each consultation component on individual clinicians. In order to test whether the observed effects were statistically significant for a given clinician, one would need to fit separate multilevel models for each of the 5 outcome variables for each clinician (a total of 60 separate models), which was beyond the scope of this project. Also, those separate individual multilevel models would not account for between-participant variation, which is a major strength of the two-level multilevel models used in this analysis. Although we hoped to include a third level of nesting (i.e., agency-level effects such as how the rurality of agency #1 affects estimates), our sample size was too small to do so.

Aim 2: Relative usability of each consultation component. We examined statistical differences among mean ratings of each consultation component (i.e., training activity) on the

Implementation Strategy Usability Scale. Usability ratings were averaged for each consultation condition for each clinician and then examined using a repeated measures one-way ANOVA. Questionnaires from all 6 agencies were utilized for this analysis.

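### The Aim 1 visual analysis judges level on raw weekly agency means, so a change in which clinicians held sessions can distort one agency's phase change, mainly by masking a real shift

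*Combined protocol and SAP*

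**What the plan says.** Under Visual Analysis for Aim 1, the plan analyses each of the 3 agencies with sufficient baselines as a single series, "using weekly data averaged across all clinicians at the agency". It states that "change in level was the main indication of a significant finding", although a clear shift in trend direction may also count. It then adds: "This effect needed to be replicated across all 3 agencies (inter-case replication) for the functional relation to be tentatively confirmed".

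Four other places bear on this.

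- Design overview: "Groups of 3-5 clinicians were recruited by each agency leader", and each consultation condition lasts 4 weeks.
- Data Collection for Observational Measures of Clinician Fidelity: in these 3 agencies, 76 of 299 scheduled sessions were cancelled. Fidelity is scored from recorded sessions, so a clinician without a session in a given week has no score that week.
- Methodological challenge with the baseline phase: losses were uneven. Baselines in Agencies 5 and 6 were extended by a week for "clinicians who had multiple cancellations in the baseline period to acquire at least 2 usable baseline sessions".
- Multilevel modeling for Aim 1: each clinician has a random intercept, so the sponsor expects baseline fidelity to differ between clinicians.

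The plan gives no rule for weeks in which some clinicians have no score. It states no minimum number contributing, no carry-forward and no within-clinician comparison for the visual analysis.

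**The concern.** If the weekly mean is taken over whoever held a session, it mixes two things: how well clinicians performed and which clinicians were present. With so few clinicians per agency, one absence carries real weight. Suppose four clinicians always score 50, 60, 70 and 80. The agency mean is 65. If the lowest scorer has no session during a phase, it becomes (60 + 70 + 80)/3 = 70, a rise of 5 points with no change in anyone's practice.

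The visual rule uses exactly this kind of level change to decide whether each hypothesis is tentatively confirmed or rejected. The multilevel model's clinician intercepts do not enter that rule. At stake are the reading of single phase changes within an agency and, because all 3 agencies must agree, the overall verdict on a component.

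**Working it through.** **Inputs from the documents**
- Cancellation: 76/299 = 0.254, which reproduces the stated 25.4%.
- Clinicians: the plan says that individual models for 5 outcomes would total 60, so 60/5 = 12 clinicians, or 12/3 = 4 per agency on average (range 3 to 5 by design).
- Weeks per consultation condition: 4.

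**Assumptions, none given in the documents**
- Between-clinician SD of 10, 15 or 20 adherence points.
- Independent cancellations and one scheduled session per clinician per week.
- Means taken over observed clinicians only.
- Two adjacent phases of 4 weeks each (baselines differ in length).
- 5 points as a visible level change.

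**1. Complete weeks.** P(all k clinicians contribute) = (1 − 0.254)^k, which is 41% for k = 3, 31% for k = 4 and 23% for k = 5. For k = 4, the chance that a 4-week phase has at least one incomplete week is 1 − 0.309^4 = 99%.

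**2. Shift from composition alone.** At least 100,000 phase changes were simulated per setting, with constant clinician scores, no consultation effect and no measurement noise. The difference is the mean of the weekly agency means in one phase minus that in the other. For k = 4:

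| Between-clinician SD | SD of phase difference | Shift of 5 points or more, either direction |
|---|---|---|
| 10 | 2.5 | 6% |
| 15 | 3.8 | 16% |
| 20 | 5.0 | 26% |

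As a closed-form check, if one of four clinicians misses a whole phase, the shift has SD × √(1/3 − 1/4) = 0.289 × SD, or 2.9, 4.3 and 5.8 points. If cancellations cluster by clinician and phase (beta-distributed cancellation probability with mean 0.254 and concentration 2), the last column rises to about 13%, 26% and 37 to 38%.

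**3. False confirmation in all 3 agencies.** With k = 4 and random cancellation, a spurious rise of at least 5 points has probability of about 0.03, 0.08 and 0.13 in one agency. Cubing the unrounded values gives about 0.002%, 0.05% and 0.2%. The largest value in any setting run (SD 20, 3 clinicians, clustered cancellation) is about 0.8%.

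**4. Masking.** Let every clinician truly rise by 8 points, with no other noise. One agency shows less than 5 points when its composition shift is below −3, which has probability q of about 0.095, 0.172 and 0.227. At least one of 3 agencies then falls short with probability 1 − (1 − q)^3:
- SD 10: 1 − 0.905^3 = 26%
- SD 15: 1 − 0.828^3 = 43%
- SD 20: 1 − 0.773^3 = 54%

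For a true rise of 10 points, the figures are about 8 to 9%, 22% and 34%.

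**5. Sensitivity to the one-session assumption.** 299/12 is about 25 scheduled sessions per clinician. Over roughly 18 to 22 weeks of baseline plus consultation, that is 25/22 to 25/18, or about 1.1 to 1.4 per week. If a fraction f of weeks (0.13 to 0.38) held two sessions, absence is (1 − f)(0.254) + f(0.254)², or 23% down to 18%. Complete weeks for k = 4 become (1 − 0.23)^4 = 35% to (1 − 0.18)^4 = 45%. At SD 10, a shift of 5 points or more falls from 6% to between 3% and 5%. The figures in steps 1 to 4 are therefore upper bounds in this respect.

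**The case against.** A reader might infer that composition changes could readily produce a falsely confirmed functional relation. The documents do not support that. The same spurious shift would have to occur in all 3 agencies, and component order is randomised by agency, so chance cancellations would have to line up with the same component each time. Step 3 shows how unlikely this is. This objection stands, and it removes most of the false-positive concern. It does not help with masking, because the rule that protects against false confirmation lets one distorted agency block a true one.

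A reader might also take it as established that the weekly mean used only the clinicians seen, or that no clinician-level plots exist. Neither can be shown. The first is an inference from the absence of any described imputation, and the figures are not available in the text.

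The multilevel model works on clinician-level data with random intercepts and so offers a cross-check on the same outcomes. But it is a separate analysis that estimates change from baseline, and nothing in the visual section lets it correct a judgement between adjacent conditions.

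The plan's review of stability and variability would reveal some composition noise as week-to-week scatter. It would be less likely to reveal a clinician missing for most of a phase. Finally, the sizes rest on assumed SDs and a 5-point cut-off, and they concern adherence, which is one of five outcomes. The four coaching competency subscales were not quantified.

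**Conclusion.** The weakness is real but limited. A raw agency mean over a changing set of about 4 clinicians can shift with no change in any clinician, by an SD of about 2.5 to 5.0 adherence points between phases if clinicians differ with an SD of 10 to 20. The main consequence is a misread phase change in one agency, or a real effect masked there and so left unconfirmed: 26% to 54% for a true 8-point rise under the stated assumptions. Full false confirmation is rare, and the documents give no ground for saying that any reported conclusion is wrong. The result rests on observed-only averaging, the assumed SDs and cut-off, and one session per clinician-week, which overstates absence if some clinicians had several. This is a cheap improvement to the method and does not invalidate the analysis.

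**What to change.** For each pair of adjacent conditions, compute each clinician's mean in each phase, take the within-clinician change, and average these changes over clinicians observed in both phases. Base the level judgement on that average. Beside the raw agency plot, show clinician-level panels and the number of clinicians contributing each week, and state how weeks with missing clinicians are handled.

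Do not instead centre each score on the clinician's mean over all sessions, because that attenuates real effects when sessions are unevenly spread across phases. Take a true rise of 20 points with one of four clinicians unseen in the first phase and sessions otherwise balanced. The three complete clinicians have centred values of −10 and +10, and the fourth has 0 in the second phase only. The series moves from −10 to (3 × 10 + 0)/4 = 7.5, an apparent rise of 17.5. The within-clinician change gives the full 20.

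The cost is a sentence or two in the plan and a re-plot of existing data. The downside is that a clinician seen in only one of two adjacent phases drops out of that comparison, so it rests on slightly fewer data.

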Statistical Analysis. An overview the statistical analysis used for each aim is presented in this section. Recent advances in statistical modeling have resulted in the specification of multilevel models that can provide effect sizes for each treatment element while also accounting for the specific features of single-case experimental designs (e.g., handling auto-correlation among consecutive datapoints, correcting for design-specific error structures). These advances have resulted in statistical packages in the R statistics platform (e.g., *sdhlm*). These tools were used to analyze results for Aims 1, 3, and 4. Specific model parameters are presented in the Results section.

Multilevel modeling for Aim 1: Effects of the group consultation model and each consultation component on clinician manual adherence and parent coaching competency. Only data from the 3 agencies with sufficient baseline data were used for Aim 1 analysis. We examined the effects of individual components of the group consultation model (i.e., consultation training activities) on clinician fidelity (i.e., manual adherence, parent coaching competency). To do so, we utilized 2-level multilevel models to estimate the change in level from the average baseline fidelity score to the average fidelity level for each consultation training activity condition (i.e., changes in level from baseline to each consultation condition). For example, the model estimated the magnitude of change from the Baseline level to the Feedback level, and whether the change was statistically significant. Specific model parameters for all models are presented in the Results section.

The models provide two sets of estimates: 1) the average effect of each consultation component on fidelity scores *averaged across clinicians* (i.e., results from the 2-level model),

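### The Aim 1 visual rule has no verdict between confirmed and rejected, so a component shown in only 1 or 2 of the 3 agencies is by implication rejected, although partial replication is weak evidence of no effect

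*Combined protocol and SAP*

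**What the plan says.** The Data Analytic Plan gives Aim 1 two analyses of the same data: only "3 agencies with sufficient baseline data were used for Aim 1 analysis".

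**Visual analysis for Aim 1.** Weekly scores are averaged over the clinicians at each agency, and each condition is compared with the one next to it. Hypotheses of a functional relation are "tentatively confirmed or rejected based on whether the consultation component was associated with a change in level". On replication the section says: "This effect needed to be replicated across all 3 agencies (inter-case replication) for the functional relation to be tentatively confirmed". The reason given is that "recommendations for interpreting single-case designs suggest that an effect should be replicated across at least 3 cases". Change in level is the main criterion, but of a clear shift in trend direction the section says that "this was also used when determining which phase changes were considered significant". It then explains that, without replication within an agency, a positive finding can be no more than tentative. It states no corresponding caution for a negative finding and no third verdict.

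**Multilevel modeling for Aim 1.** A two-level model estimates each component's change from baseline, pooled across clinicians. In the plan's example, "the model estimated the magnitude of change from the Baseline level to the Feedback level, and whether the change was statistically significant". The plan does not say how the visual verdict and the model result are weighed if they differ.

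**The concern.** Aim 1 is meant to identify the active ingredients of consultation. The three-demonstration standard cited under summative visual analysis sets how much is needed to count as positive evidence. Falling short of it means that an effect has not been demonstrated; it does not show that the effect is absent. A rule with two named verdicts loses that distinction.

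With exactly three usable agencies, the cited minimum of three cases becomes three out of three, with no slack. One agency failing to show a real effect is quite possible here:

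- Each component is delivered for only 4 weeks.
- In these three agencies 76 of 299 scheduled sessions (25.4%) were canceled, which makes the weekly means noisier.
- Two of the four competency subscales have inter-rater ICCs of 0.63 and 0.69 (Table 7).
- Component order is randomized by agency and the visual comparison is with the adjacent condition, so the same component may be judged against different predecessors.

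At stake is how a mixed result is reported. A clear effect in two agencies and none in the third could appear under the same label as no effect anywhere, possibly beside a multilevel estimate that is statistically significant.

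**Working it through.** The plan states no power or error rate for the visual rule, so there is no figure of its own to reproduce. The calculation below is illustrative.

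**Inputs**
- Agencies: 3, all needed for confirmation (visual analysis for Aim 1).
- q, the probability that one agency shows a real effect: assumed, not in the documents. Range 0.6 to 0.95.
- Agencies independent at first: assumed, relaxed in step 2.

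**Step 1. Independent agencies.** P(confirmed) = q³. P(not confirmed) = 1 − q³. P(at least 2 of 3) = q³ + 3q²(1 − q).

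| q | Confirmed (3 of 3) | Not confirmed | At least 2 of 3 |
|---|---|---|---|
| 0.60 | 21.6% | 78.4% | 64.8% |
| 0.70 | 34.3% | 65.7% | 78.4% |
| 0.80 | 51.2% | 48.8% | 89.6% |
| 0.90 | 72.9% | 27.1% | 97.2% |
| 0.95 | 85.7% | 14.3% | 99.3% |

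An 80% chance of confirmation needs q = 0.8^(1/3) = 0.928. At q = 0.8, exactly 2 of 3 has probability 0.896 − 0.512 = 38.4%, so most failures to confirm a real effect (38.4 of 48.8 percentage points) are 2-of-3 results.

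**Step 2. Dependent agencies.** Use a beta-binomial with mean 0.8 and intra-class correlation ρ. With s = 1/ρ − 1 and a = 0.8s, P(confirmed) = a(a+1)(a+2) / [s(s+1)(s+2)]. For ρ = 0.5: s = 1, a = 0.8, and 0.8 × 1.8 × 2.8 / (1 × 2 × 3) = 4.032 / 6 = 0.672.

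| ρ | Not confirmed at q = 0.8 |
|---|---|
| 0 | 48.8% |
| 0.1 | 45.1% |
| 0.2 | 41.8% |
| 0.3 | 38.6% |
| 0.5 | 32.8% |
| 1 | 20.0% |

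**Step 3. What a mixed count says.** Suppose also, as a further assumption, that an agency shows an apparent change with probability 0.2 when the component does nothing, with agencies independent.
- 2 of 3: real effect 3 × 0.8² × 0.2 = 0.384; no effect 3 × 0.2² × 0.8 = 0.096. The ratio is 4 to 1 in favour of a real effect.
- 1 of 3: real effect 3 × 0.8 × 0.2² = 0.096; no effect 3 × 0.2 × 0.8² = 0.384. The ratio is 4 to 1 against.
- 0 of 3: real effect 0.2³ = 0.008; no effect 0.8³ = 0.512. The ratio is 64 to 1 against.
- 3 of 3 with no effect: 0.2³ = 0.8%, so the strict rule guards well against false confirmation.

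On these assumptions the three results short of confirmation carry very different evidence, and a single label hides that. The count itself should be reported.

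**The case against.** The strongest case on the other side has five parts.

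1. **No sentence assigns 1 of 3 or 2 of 3 to rejection.** The three-agency requirement is attached only to confirmation, and the word tentatively can be read as covering rejection as well. This is fair: the assignment is an inference. But no other verdict is named, so at best mixed results are unclassified, and the same clarification is needed.

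2. **Rejection concerns the functional relation, not the component.** A reader might infer that a working component will be declared inactive. The documents do not say so. What is rejected is a hypothesis within the visual analysis.

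3. **Aim 1 also has the multilevel model.** An effect visible in two agencies can still be estimated and tested there. This stands, and it means that the visual verdict need not be the study's conclusion. It does not settle the matter, because the model compares with baseline while the visual analysis compares adjacent conditions, and the plan does not say which governs or how a conflict is read.

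4. **The percentages rest on assumed inputs.** This stands. A reader might take away that a real effect is missed about half the time; that holds only near q = 0.8 with roughly independent agencies. A further step, multiplying across three components to say that all would be confirmed in only 13% of trials (0.512³), needs independence between components read from the same agency series, where one phase is the comparator for the next. The documents do not support it.

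5. **Detection may be better than the cancellation rate suggests.** Weekly scores are averaged over clinicians, recruited in groups of 3 to 5, so a canceled session usually adds noise to a weekly mean without removing it. A clear trend shift can also count. Both points argue for a higher q, but neither fixes its value.

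Requiring 3 of 3 for confirmation is a legitimate guard against false positives and is not disputed here.

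**Conclusion.** The point holds as a matter of labelling and interpretation. The visual rule names two verdicts and reserves one for complete replication, so partial replication falls by implication under rejection, which is stronger than the evidence allows. For illustration, with independent agencies the rule fails to confirm a real effect 66%, 49%, 27% or 14% of the time for assumed q of 0.7, 0.8, 0.9 or 0.95; at q = 0.8 the figure falls from 49% towards 20% as dependence between agencies rises. None of these inputs is in the documents, so the range shows that non-confirmation of a real effect can be common. It does not estimate how often that happened here.

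The documents do not support saying that the plan declares working components inactive, or that the Aim 1 conclusion rests on the visual verdict alone.

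**What to change.** - Keep 3 of 3 agencies for tentatively confirmed.
- Replace rejected with not demonstrated or inconclusive for 1 or 2 of 3, and with no visual evidence for 0 of 3.
- Report the count out of 3 for every component and outcome. If the visual analysis covers the same 5 outcomes as the models, that is 3 × 5 = 15 cells.
- Set each count beside the multilevel estimate and its interval for that component, and state how disagreement is interpreted, given that one analysis compares adjacent conditions and the other compares with baseline.
- State that no component is concluded to be inactive from the visual verdict alone. The documents define no minimum meaningful gain, so a formal claim of no effect would need one to be set and justified first; the changes above do not depend on it.

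The cost is a reworded rule and one small table from graphs and models already planned; no new data are needed. The downside is that some components will be reported as inconclusive where the present wording gives a settled answer. Grouping 1 of 3 with 2 of 3 is a judgment, which is why the count should be shown with the label.
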